## J. COVID-19 Pandemic Impacted Subjects Assessment

Subjects who are impacted by COVID will be excluded in the Per-protocol Set.

The number of subjects who missed visits due to COVID-19 and the impacts ("Quarantined", "Site temporarily closed", "Unable to commute to clinic", "Other") due to the missing visits will be summarized by treatment and overall, and a by-subject listing will be provided. Moreover, the number of subjects who have COVID-19 related TEAEs or COVID-19 related protocol deviations will be reported in the disposition table. Any major COVID-19 related protocol deviations will be summarized and listed.

## Appendix I

Visit	Screening		Treatment (Day 1 to Day 113)				Follow-up (Day 127 to Day 169)			
	Day -35 to -1	Day 1	Day 15	Day 29	Day 57	Day 85	Day 113	Day 127/E/T/Discon	Day 141	Day 169
Study Day										
Week Number			Week 2	Week 4	Week 8	Week 12	Week 16	Week 18	Week 20	Week 24
Visit Number	Visit 1	Visit 2	Visit 3	Visit 4	Visit 5	Visit 6	Visit 7	Visit 8	Visit 9	Visit 10
Window (day)			±2	±3	±3	±3	±3	±3	±3	±3
Informed consent	X									
Eligibility check for randomization	X	X								
Medical history	X									
Demographics	X									
Physical examination a	X	X	X	X	X	X	X	X	X	X
Height, weight, and BMI b	X							X		
TB screening	X									
Pregnancy test (females only) c	X	X		X	X	X	X	X		X
COVID-19 test d	X	X								
Clinical laboratory tests e , including FSH at screening f	X	X	X	X	X	X	X	X	X	X
Urinalysis	X	X		X			X	X		
Triplicate 12-lead ECG	X	X		X			X	X		
Vital signs	X	X	X	X	X	X	X	X	X	X
Fitzpatrick skin type	X									
EASI	X	X	X	X	X	X	X	X	X	X
vIGA	X	X	X	X	X	X	X	X	X	X
BSA (palm method to be used for both EASI and SCORAD)	X	X	X	X	X	X	X	X	X	X
Randomization		X								

Visit	Screening	Baseline		Treatment (Day 1 to Day 113)						Follow-up (Day 127 to Day 169)				
		Day 1	Day 15	Day 29	Day 57	Day 85	Day 113	Day 127/E/T/ Discon	Day 141	Day 169				
Study Day	Day -35 to -1													
Week Number	Visit 1		Week 2	Week 4	Week 8	Week 12	Week 16	Week 18	Week 20	Week 24				
Visit Number	Visit 2		Visit 3	Visit 4	Visit 5	Visit 6	Visit 7	Visit 8	Visit 9	Visit 10				
Window (day)			±2	±3	±3	±3	±3	±3	±3	±3				
SCORAD		X	X	X	X	X	X	X	X	X				
Daily Pruritus (PP-NIRS)		X				X								
Daily Skin Pain NRS		X				X								
ADSS		X				X								
Patient Global Assessment (PtGA)		X	X	X	X	X	X	X	X	X				X
DLQI		X	X	X	X	X	X	X	X	X				X
POEM		X	X	X	X	X	X	X	X	X				X
ACQ-5 g		X				X				X				X
Photographs i		X		X	X	X	X	X						X
Provisioning Subject e-Diary Device or Application l		X							X					X
Study drug dosing at study center k		X	X	X	X	X								
Study drug dosing daily at home k		X									X			
Daily subject e-Diary for drug dosing at home		X												
PK sampling – Blood l		X	X	X	X	X	X	X	X	X				
Tape stripping m		X		X	X	X	X	X	X	X				X
Skin microbiome samples (swab) n		X		X	X	X	X	X	X	X				X

Visit	Screening	Baseline			Treatment (Day 1 to Day 113)						Follow-up (Day 127 to Day 169)			
		Day -35 to -1	Day 1	Day 15	Day 29	Day 57	Day 85	Day 113	Day 127/E/T/Discon	Day 141	Day 169	Day 127/E/T/Discon	Day 141	Day 169
Study Day	Day -35 to -1													
Week Number	Visit 1	Week 2	Week 3	Week 4	Week 8	Week 12	Week 16	Week 18	Week 20	Week 24	Week 18	Week 20	Week 24	Week 24
Visit Number	Visit 1	Visit 2	Visit 3	Visit 4	Visit 5	Visit 6	Visit 7	Visit 8	Visit 9	Visit 10	Visit 8	Visit 9	Visit 10	Visit 10
Window (day)			±2	±3	±3	±3	±3	±3	±3	±3	±3	±3	±3	±3
Plasma Sample Collection for Biomarker Exploration o		X		X			X				X			X
Serum cytokines/chemokines and biomarker levels		X	X	X	X		X	X			X	X		X
Immunophenotyping – Blood p		X			X		X				X			X
Pharmacogenomics Cell Pellet q		X												
Study drug distribution		X	X	X	X	X								
Study drug collection/review			X	X	X	X	X				X			
Rescue therapy collection/review (on or after Day 57 if applicable)					X	X	X				X	X		X
Application of rescue therapy in e-Diary (if applicable)					X	X	X				X	X		X
Prior and concomitant medication														
AE/SAE reporting														
Ongoing from screening														
Ongoing from the time of signing the ICF (non-treatment and treatment- emergent adverse events)														

Abbreviations: ACQ=asthma control questionnaire; ADSS=atopic dermatitis sleep scale; AE=adverse event; BMI=body mass index; BSA=body surface area; DLQI=Dermatology Quality of Life Index; EASI=Eczema Activity and Severity Index; ECG=electrocardiogram; ET=Early Termination; FSH=follicle-stimulating hormone; ICF=Informed Consent Form; PK=pharmacokinetics; POEM=Patient-oriented eczema measure; PP-NRS=Peak Pruritus Numerical Rating Scale; PtGA=Patient's Global Assessment; SAE=serious adverse event; SCORAD=SCORing Atopic Dermatitis; [REDACTED]; TB=tuberculosis; vIGA=Validated Investigator Global Assessment.

Baseline assessments to be obtained pre-dose.

There are no post-dose blood draws.

- a. Full physical examination at Screening, partial physical examination at all other visits.
- b. Height and weight will be collected, and BMI calculated at Screening. Weight will be collected at follow-up.
- c. Serum pregnancy test at Screening, and urine pregnancy test at other visits.
- d. A negative COVID-19 test is required at Screening.
- e. Fasting required for labs at Baseline, Day 113 (Week 16), and Day 127/ET/Discon (Week 18). A subject should refrain from eating or drinking (except for water) for a period of at least 8 hours prior to the lab draw.
- f. FSH at Screening only for females of non-childbearing potential.
- g. The ACQ-5 instrument will only be assessed in subjects reporting a history of ongoing asthma at Screening.
- [REDACTED]
- i. Photographs will be taken at the selected sites. One or more most affected body regions, per Investigator's judgement, may be photographed.
- j. The e-Diary will be dispensed to the subject or the e-Diary application will be loaded to the subject's device at Baseline. Collection or removal of application will occur at EOS or at ET/Discon. Subjects enter e-Diary information on a daily basis for their compliance with study treatment starting Baseline/Day 1, recording daily pruritus, daily skin pain NRS, and ADSS starting at Baseline/Day 1.
- k. On Day 1, Day 15, Day 29, Day 57, and Day 85, the study drug will be administered at the study center after all other assessments are performed. All other daily drug intake will be self-administered by the subject, at home, at approximately the same time of the day through Day 112.
- l. PK blood sampling will be done pre-dose on Day 1, Day 15, Day 29 and Day 57.
- m. Tape stripping is only required for subjects in the US and Canada; tape stripping should not be performed for subjects in Poland. Tape strips will be collected from lesional and non-lesional skin pre-dose at Baseline. Tape strip samples will also be collected at the same sites sampled at Baseline on Day 29, Day 57, Day 113, and on Days 141 and 169, if applicable.
- n. Two skin microbiome samples will be collected at Baseline, one from lesional and one non-lesional skin. A skin microbiome sample will also be collected at subsequent visits at the same lesional site sampled at Baseline.
- o. Plasma blood sampling will be done pre-dose.
- p. The immunophenotyping sample is only required for subjects in the US and Canada; immunophenotyping samples should not be collected from subjects in Poland.
- q. Blood sample will be collected from subjects who have consented to participate in the genetic analysis component of the study. Participation is optional.

## Appendix II

### SAS example code for ANCOVA:

```
proc glm data=data_in;  
  by avisitn avisit;  
  class trtp(ref="vehicle") prioruse;  
  model chg = trtp base_EASI base_VIGA prioruse / solution ss3;  
  lsmeans trtp / stderr pdiff=all cov cl;  
  ods output lsmeans=lsm lsmeandiff=diff parameterestimates=pp;  
run;
```

### SAS example code for MMRM:

```
proc mixed order=internal data = data_in;  
  class usubjid trt01pn avisitn avisit prioruse;  
  model pchg = base_EASI trt01pn avisitn avisit trt01pn*avisit base_VIGA prioruse/noint  
  solution ddfm=kenwardroger;  
  repeated /type=un subject=usubjid;  
  lsmeans trt01pn*avisit /cl pdiff ;  
  ods output lsmeans=lsmeans diffs=diffs;  
run;
```

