### Sensitivity Analyses

Similar to control-based PMM-MI under MNAR, missing EASI will be imputed using the multiple imputation (MI) with analysis of covariance (ANCOVA) model as the primary analysis for time-points at which no value is observed. MI will be performed under missing at random (MAR) assumption.

The Week 16 data of each of the 100 complete imputed datasets will be analyzed using an ANCOVA model with treatment, randomization strata, and baseline EASI value included in the model, and the SAS MIANALYZE procedure will be used to generate valid statistical inferences by combining results from the 100 analyses using Rubin's formula. The example code can be found in Appendix II.

In addition to the MI method described previously, sensitivity analyses for the percent change in EASI will also be conducted using Mixed-effect Model for Repeated Measures (MMRM) without imputation. The model will include factors (fixed effects) for treatment, randomization strata, visit, treatment-by-visit interaction, and baseline EASI score. An unstructured covariance matrix will be used to model the within-patient errors. Denominator degrees of freedom will be estimated using approximation of SATTERTH. The efficacy data will be set to missing after rescue medication or procedure is used or after study withdrawal. Afterwards no imputation will be made.

The MMRM model will provide baseline adjusted least-squares (LS) means at Week 16 and at other time points for each treatment group with the corresponding standard error and the confidence interval, as well as the p values for treatment comparisons. The graph of LS-mean +/- SE by visit will be provided.

Other following sensitivity analyses will be planned for the primary estimand using the ANCOVA model mentioned above:

- In FAS, using PMM-MI and including site as a factor in the ANCOVA model.
- PP analysis set, using MI for handling missing data.
- In FAS, the LOCF and WOCF methods to handle missing data.
- In FAS, the Observed-Cases (OC) approach. No imputation for missing data at any time point. Data collected after the start of rescue will be set to missing.

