### Sensitivity Analyses

Similar to primary efficacy endpoint, missing PP-NRS will be imputed using the multiple imputation (MI) with analysis of covariance (ANCOVA) model. MI will be performed under missing at random (MAR) assumption.

The Week 16 data of each of the 100 complete imputed datasets will be analyzed using an ANCOVA model with treatment, randomization strata, and baseline PP-NRS value included in the model, and the SAS MIANALYZE procedure will be used to generate valid statistical inferences by combining results from the 100 analyses using Rubin's formula.

The percent change from baseline in PP-NRS will also be analyzed using MMRM without imputation. The model will include factors (fixed effects) for treatment, randomization strata, visit, treatment-by-visit interaction, and baseline PP-NRS score. An unstructured covariance matrix will be used to model the within-patient errors. Denominator degrees of freedom will be estimated using approximation of SATTERTH. The efficacy data will be set to missing after rescue medication or procedure is used or after study withdrawal. Afterwards no imputation will be made.

The MMRM model will provide baseline adjusted least-squares (LS) means at Week 16 and at other time points for each treatment group with the corresponding standard error and the confidence interval, as well as the p values for treatment comparisons. The graph of LS-mean +/- SE by visit will be provided.

Other following sensitivity analyses will be planned for the key secondary using the ANCOVA or logistic model mentioned above, as applicable:

- In FAS, using PMM-MI and including site as a factor in the ANCOVA model.
- PP analysis set, using MI for handling missing data for all key secondary endpoints.
- In FAS, the LOCF and WOCF methods for handling missing data for continuous endpoints.

- In FAS, the TF method for handling missing data for binary endpoints.
- In FAS, the Observed-Cases (OC) approach for all endpoints. No imputation for missing data at any time point.

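### The example MMRM code names no visit in REPEATED and asks for Kenward-Roger where the text says Satterthwaite: a minor mismatch, which moves the Week 16 sensitivity estimate only if skipped visits have no row

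*SAP*

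**What the plan says.** SAP VI.C (Sensitivity Analyses) sets out the EASI model: "The model will include factors (fixed effects) for treatment, randomization strata, visit, treatment-by-visit interaction, and baseline EASI score". On covariance it says "An unstructured covariance matrix will be used to model the within-patient errors", and on inference "Denominator degrees of freedom will be estimated using approximation of SATTERTH". SAP VI.D.1 applies the same approach to itch: "The percent change from baseline in PP-NRS will also be analyzed using MMRM without imputation", again with unstructured covariance and Satterthwaite. Both sections set values after rescue or withdrawal to missing and do not impute them.

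The example MMRM code in SAP Appendix II has the mean model "model pchg = base_EASI trt01pn avisitn avisit trt01pn*avisit base_VIGA prioruse/noint", then "solution ddfm=kenwardroger", then "repeated /type=un subject=usubjid". It differs from the text in one respect and leaves another open:

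- Degrees of freedom: Kenward-Roger in the code, Satterthwaite in the text.
- Covariance indexing: the type is unstructured, as in the text, but no effect in REPEATED ties a row to a visit.

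Visit also enters MODEL twice, as `avisitn` and as `avisit`.

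The SAP foresees gaps. The control-based imputation paragraph in SAP IV.D.2 has a separate step for intermittent missing data. SAP IV.C treats a PP-NRS week with fewer than three diary entries as missing. Neither document says whether the MMRM input data set keeps a row for a missed visit.

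**The concern.** An unstructured matrix has one variance per visit and one covariance per pair of visits, so each row has to be tied to the right visit. With no repeated effect, PROC MIXED uses row order within subject. Take a subject seen at Weeks 2, 4, 12 and 16 whose Week 8 visit has no row. Week 12 becomes the third row and takes the Week 8 place; Week 16 becomes the fourth and takes the Week 12 place. The mean model still labels the visits correctly, but the weights that combine the data across visits are wrong for that subject, and the estimated matrix mixes visits.

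At stake is the MMRM check on the primary endpoint and on the PP-NRS key secondary endpoint, with the LS-mean-by-visit graphs. A sensitivity analysis should not depend on how the data set is laid out. The two degrees-of-freedom methods also leave two versions of the same prespecified analysis.

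**Working it through.** **Trial size.** SAP III.C gives 60 evaluable subjects per group and 10% dropout: 60 / (1 − 0.10) = 66.7, rounded up to 67, and 4 × 67 = 268. This reproduces the SAP total and sets the size of the simulation. The effect size, SD and power behind the 60 are redacted, so the inputs below are assumptions.

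**Simulation of the indexing.** From the SAP: 67 per group, four groups, five post-baseline EASI visits to Week 16. Assumed: SDs of percent change rising over the visits as 22, 27, 32, 35 and 38 points; correlation 0.85 between adjacent visits, decaying as a power; a Week 16 effect of −15 points for 400 mg; about 10% monotone loss; and 2%, 5% or 10% of earlier visits skipped with no row. Each data set was fitted twice by REML with an unstructured matrix, indexed first by visit and then by row order. Shift = row-order estimate minus visit-indexed estimate of the Week 16 difference, 400 mg versus placebo. There were 100 runs per scenario.

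| Earlier visits skipped | Subjects with a gap | Mean absolute shift | Mean signed shift | SE, visit-indexed | SE ratio | Significance call changed |
|---|---|---|---|---|---|---|
| 2% | 7% | 0.80 | +0.10 | 6.72 | 0.993 | 2% |
| 5% | 17% | 1.31 | −0.29 | 6.73 | 0.984 | 6% |
| 10% | 32% | 1.65 | +0.05 | 6.74 | 0.969 | 11% |

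- Size relative to the SE: 0.80/6.72 = 0.12, 1.31/6.73 = 0.19 and 1.65/6.74 = 0.24.
- Direction: the SDs of the shift were 1.07, 1.62 and 2.10, so with 100 runs the Monte Carlo SEs of the mean signed shift are 0.11, 0.16 and 0.21. None of the three means is two of these from zero.
- Changed calls: the visit-indexed fit was significant in 57% to 68% of runs, so many runs lie near the threshold and the last column would be lower with a clearer result.
- No intermittent gaps: the shift is exactly 0, because row order and visit order coincide. Three check runs confirmed it. The same holds when a missed visit stays as a row with a missing response, in visit order.

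**Degrees of freedom.** The method leaves the estimate alone. With 240 df (assumed), a t of 1.97 gives p = 0.050. If Kenward-Roger inflated the SE by 1% (assumed), t becomes 1.97/1.01 and p = 0.052; at 2%, p = 0.055. The critical value hardly depends on the df here: 1.984 at 100 df and 1.969 at 260.

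**Duplicate visit term.** `avisitn` and `avisit` carry the same information, so the second adds nothing to the mean model and leaves treatment differences within a visit unchanged.

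**The case against.** The strongest reply is that the harm depends on a data layout that the documents never describe. Values after rescue are to be set to missing, and a thin diary week is to be treated as missing; both wordings fit a data set that keeps the row. Loss through dropout or rescue is trailing and misaligns nothing. This stands: the effect is a possibility, not an established fact.

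The code is also labelled as an example, and it has the marks of a template (the ANCOVA example uses a vehicle reference level in a trial of placebo tablets). The text in SAP VI.C and VI.D.1 can be taken to govern. The MMRM is one of seven sensitivity analyses listed for the primary endpoint in SAP VI.B, and it may differ from the control-based primary analysis simply because the missing-data assumptions differ. All of this limits the consequence.

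For PP-NRS, gaps need not be common. If 20% of entries were missed independently (an assumption), the chance of fewer than three in seven is 0.2^7 + 7 × 0.8 × 0.2^6 + 21 × 0.8^2 × 0.2^5 = 0.0047 per week. Over the 15 weeks before Week 16 that gives 1 − (1 − 0.0047)^15, or about 7% of subjects with a gap; clustered non-response would raise it. The table above covers EASI only.

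What remains is that the text and code disagree on one setting, and that alignment rests on an unstated property of the data set.

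**Conclusion.** The point holds as a minor text-to-code mismatch. If intermittently missed visits have no row, the Week 16 sensitivity estimate moves by about 0.8 to 1.7 points on average in no consistent direction, against an SE of about 6.7, and that SE is about 1% to 3% too small. These sizes rest on assumed SDs, correlations, effect and skip rates. If rows are kept in visit order, or loss is monotone only, the effect is nil. The primary control-based imputation with ANCOVA and its dose-order testing are not touched.

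Three stronger readings are tempting, and the documents do not support them:

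- A reader might infer that the code fits a different model, so the Week 16 result is shifted. The mean terms and the unstructured type match the text, and no passage says that rows are dropped.
- A reader might infer that the degrees-of-freedom conflict adds to the shift. It cannot; it affects only the SE, interval and p-value.
- A reader might infer from "lsmeans trtp / stderr pdiff=all cov cl", which has no observed-margins option, that the arm means are wrong because prior biologic users count for half although protocol 6.3 caps them at approximately 20%. Equal weighting is a conventional LS mean, and the SAP promises no other. The between-arm difference, which is the summary measure in SAP II.A, is unchanged because the model has no interaction of treatment with prior use.

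**What to change.** Make three edits to the example MMRM code in SAP Appendix II:

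1. Write `repeated avisit / type=un subject=usubjid;`. Alignment then no longer depends on whether a missed visit has a row.
2. Use one degrees-of-freedom method in text and code. `ddfm=satterth` matches SAP VI.C and VI.D.1 as they stand.
3. Keep a single visit variable in MODEL, as tidying.

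No change to the LSMEANS weighting is needed. SAP I.B allows changes until unblinding. The edits take minutes and alter no estimand, endpoint or primary result.

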### SAS example code for MI (MAR):

```
proc mi data =data_in out=data_out seed =1277282 nimpute=100 min= 0; by trt01p;  
  mcmc impute = monotone; var week2-16;  
run;
```

### SAS example code for PMM-MI (NMAR):

#### EASI\_PP-NRS

```
proc mi data =data_in out =data_out seed=1277282 nimpute = 1 min=0 by _imputation_;  
  class trt01p base_VIGA prioruse;  
  var base_EASI week2-16;  
  monotone reg(week16 = base_EASI week2-12 trt01p base_VIGA prioruse);  
  mnar model(week16/ modelobs=(trt01p='placebo'));  
run;
```

VIGA

```
proc mi data =data_in out =data_out seed=1277282 nimpute = 1 min=0 max=4
  by _imputation_;
  class trt01p base_VIGA prioruse;
  var base_VIGA week2-16;
  monotone_logistic(week16 = week2-12 trt01p base_VIGA prioruse);
  mnar model(week16/ modelobs=(trt01p='placebo'));
run;
```

SAS example code for imputed results combinations:

```
proc glm data = data_mi;
  model week16 = base_EASI week2-12 trt01p base_VIGA prioruse;
  by _imputation_;
  ods output ParameterEstimates=mxparms;
run;

proc mi analyze parms=mxparms;
  class trt01p;
  modeleffects Intercept base_EASI week2-12 trt01p base_VIGA prioruse;
run;
```

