### A. Estimand

The main estimands associated with the primary and key secondary endpoints to support regulatory decisions are described in the following table:

Attribute	Description
Treatment	RPT 193-02 (50mg, 200mg, 400mg) and Placebo
Population	Adult subjects with moderate-to-severe AD as defined by the inclusion/exclusion criteria
Endpoint	
Primary Endpoint
 
 
% change in Eczema Area Severity Index (EASI) from baseline at Week 16
 
 
Key Secondary Endpoints
 
 
% of subjects achieving a Validated Investigator Global Assessment (vIGA) score of 0 or 1 at Week 16
 
% of subjects achieving EASI-75, defined as a 75% reduction in EASI from baseline to Week 16
 
% change from baseline in PP-NRS from an itch daily e-Diary at Week 16.
 

Intercurrent Events	
 
Early termination of study treatment: Subjects who discontinue from the study treatment prior to Week 16 will be analyzed by the treatment policy strategy, i.e., all data collected after termination of study treatment but prior to rescue medication will be included in the analysis. Missing post discontinuation values will be imputed according to details provided below.
 
Use of rescue medications: Subjects who use rescue medication during the 16-week treatment period will be analyzed by the hypothetical strategy. All EASI/vIGA/PP-NRS scores collected after the start of rescue medication will be set to missing. The missing data after the use of rescue medication will be imputed to follow a similar profile as the placebo group.
 

Population-level Summary	
Primary Endpoint
 
 
Difference in mean percent change from baseline in EASI score between each RPT193 dose and placebo at Week 16.
 
 
Key Secondary Endpoints
 
 
Difference in percentage of subject achieving vIGA of 0 or 1 between each RPT193 dose and placebo at Week 16.
 
Difference in percentage of subject achieving EASI-75 between each RPT193 dose and placebo at Week 16.
 
Difference in mean percent change from baseline in PP-NRS
 

	between each RPT193 dose and placebo at Week 16.
--	--

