### C. Primary Efficacy Analysis

The primary endpoint is the percent change in EASI from baseline to Week 16. The primary analysis will be based on the FAS and will use control-based PMM-MI to handle missing data.

The primary efficacy endpoint will be analyzed with an ANCOVA model. The model will include treatment group (each RPT193 dose vs. placebo), the randomization stratification factors of baseline vIGA score (3,4), and prior dupilumab or tralokinumab use (yes or no), and baseline EASI score as a covariate.

For each imputed dataset the least square (LS) mean, and LS mean difference in the percent change from baseline between each RPT193 dose level and placebo along with the corresponding estimated standard error will be reported. These results will be combined in PROC MIANALYZE using Rubin's formula and the resulting p-value will be used for inference at the 0.05 level of significance. The LS mean and LS mean difference along with the 95% confidence interval (CI) and p-value will be reported.

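### The SAP's only example code for pooling imputed results models the raw Week 16 score, adjusts for Week 2-12 scores and outputs no LS mean differences, contradicting the primary analysis in its own text.

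*SAP*

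**What the plan says.** **Text.** SAP Section II.A gives the summary measure for the primary endpoint as "Difference in mean percent change from baseline in EASI score between each RPT193 dose and placebo at Week 16". Section VI.C specifies an ANCOVA: "The model will include treatment group (each RPT193 dose vs. placebo), the randomization stratification factors of baseline vIGA score (3,4"), then prior dupilumab or tralokinumab use, then baseline EASI as covariate. LS means and LS mean differences in percent change, with standard errors, are taken from each imputed dataset. "These results will be combined in PROC MIANALYZE using Rubin's formula and the resulting p-value will be used for inference" at the 0.05 level. The sensitivity paragraph of the same section repeats the covariates for the missing-at-random version: each completed dataset "will be analyzed using an ANCOVA model with treatment, randomization strata, and baseline EASI value included in the model". It then speaks of "combining results from the 100 analyses using Rubin's formula. The example code can be found in Appendix II".

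**Code.** Appendix II has one block that combines imputed results. Its PROC GLM step reads "model week16 = base_EASI week2-12 trt01p base_VIGA prioruse" and its pooling step reads "modeleffects Intercept base_EASI week2-12 trt01p base_VIGA prioruse". The imputation model a few lines above reads "monotone reg(week16 = base_EASI week2-12 trt01p base_VIGA prioruse").

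**Route from text to code.** The primary paragraph of Section VI.C does not cite Appendix II. Two other places do: the sensitivity paragraph just quoted, and Section IV.D.2, where the control-based imputation used for the primary analysis is described.

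**The concern.** The analysis model in the pooling block has the same right-hand side as the imputation model, and was apparently carried over from it. Week 2-12 scores belong in the imputation step, where they help predict a missing Week 16 value. In the analysis step they are post-randomisation variables that treatment can change, so adjusting for them removes the part of the treatment effect already visible by Week 12.

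The primary comparison also opens the 400, 200, 50 mg testing sequence in SAP Section IV.G. If code and text still differ at unblinding, someone must choose between them with results in view. Section I.B says the SAP governs the analysis, but no passage says whether its text or its code prevails where they disagree.

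**Working it through.** **1. Text and code side by side.**

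| Element | Text (SAP II.A, VI.C) | Pooling block (SAP Appendix II) |
|---|---|---|
| Outcome | Percent change in EASI at Week 16 | `week16` |
| Baseline terms | Baseline EASI, baseline vIGA, prior use | Same |
| Post-randomisation terms | None | Weeks 2-12 |
| Quantity pooled | LS means and LS mean differences | Regression parameters |
| Treatment as a class factor in the model | Implied by each dose vs placebo | No CLASS statement in PROC GLM |

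`week16` must be the raw score. It is the variable imputed with a minimum of 0, a floor that would rule out any improvement on a percent-change scale, and no percent change is derived between imputation and PROC GLM.

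No other Appendix II block supplies the stated analysis. The ANCOVA example has baseline-only covariates, but it models `chg`, names a vehicle reference level in a placebo-controlled trial, and has no pooling step. The MMRM example uses `pchg`, which fits the text, but it works without imputation. The appendix thus uses three different outcomes for one endpoint.

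**2. The one planning figure that can be checked.** SAP Section III.C: 60/(1 - 0.10) = 66.7, rounded up to 67 per group; 4 x 67 = 268. This reproduces. The effect size and SD behind the 60 are redacted.

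**3. What the block would estimate if made to run with its terms kept.** Let d16 be the Week 16 effect, d the vector of effects at baseline (zero) and Weeks 2, 4, 8 and 12, and b the regression weights of Week 16 on those five scores. Then

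coefficient = d16 - b'd, and share kept = (d16 - b'd)/d16.

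The documents give no visit correlations and no effect time course, so every input from here on is assumed.

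- AR(1) correlation r: only Week 12 carries weight, so share kept = 1 - r x (Week 12 effect/d16). For r = 0.9 and an early effect (Week 12 share 1): 1 - 0.9 = 0.10. For r = 0.7 and a ramp (0.9): 1 - 0.63 = 0.37. For r = 0.5 and a linear build-up (0.75): 1 - 0.375 = 0.625. For r = 0.9 and a late effect (0.5): 1 - 0.45 = 0.55.
- Compound symmetry r: each prior score has weight r/(1 + 4r). For r = 0.5 the weight is 0.5/3 = 0.167. For an early effect (0.6 + 0.9 + 1 + 1 = 3.5): 1 - 3.5 x 0.167 = 0.42. For r = 0.3 the weight is 0.3/2.2 = 0.136. For a late effect (0 + 0.05 + 0.2 + 0.5 = 0.75): 1 - 0.10 = 0.90.

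Over 48 combinations (r from 0.3 to 0.9, both structures, four time courses) the share kept runs from 0.10 to 0.90.

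**4. Illustrative power.** Assume an effect of 0.516 SD, which gives 80% power with 60 per arm in a two-sample t-test, and analyse 67 per arm. The figures isolate the Week 2-12 adjustment.

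| Assumed scenario | With Week 2-12 terms | Baseline terms only |
|---|---|---|
| AR(1) 0.9, early | 0.10 | 0.96 |
| AR(1) 0.7, ramp | 0.32 | 0.85 |
| AR(1) 0.5, linear | 0.56 | 0.84 |
| CS 0.5, early | 0.34 | 0.93 |
| CS 0.3, late | 0.84 | 0.88 |
| AR(1) 0.9, late | 0.96 | 0.96 |

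**5. Both departures together, on the EASI scale.** This is a simulation with complete data, assumed mean baseline EASI of 27, and a true difference of about 18.5-19.1 percentage points. Raw `week16` without the Week 2-12 terms gives 5.0-5.2 EASI points, as expected from 0.185 x 27 = 5.0 and 0.191 x 27 = 5.2. With those terms the coefficient is 0.5-4.3 EASI points. Power is 0.12-0.97, against 0.84-0.87 for the text's model; it is higher than the text's model in 3 of 20 scenarios, all with a late effect. With no effect at any visit, rejection was 4.6%-5.2% for the block's model and 5.0%-5.3% for the text's.

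**The case against.** The pre-specified analysis is not ambiguous. The text names the endpoint, the summary measure, the covariates, the quantity pooled and the p-value used for inference. The block is headed as example code, and the primary analysis paragraph does not cite it. It is also not a working rival analysis. Treatment is a text variable (the imputation code selects the level placebo by name), so PROC GLM without CLASS cannot fit it; a numeric code would give one slope, not three dose contrasts. The week list is shorthand, and there is no LSMEANS statement. A programmer would have to rewrite the block, most naturally from Section VI.C. The leftover vehicle label further suggests template text.

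Most of this stands. A reader might infer that the primary p-value will come from the wrong model, or that the trial will lose a particular amount of power. The documents support neither. The scenario results reflect a chosen grid, not probabilities for this trial, and the simulation has no missing data, so it does not exercise the imputation.

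What does not fall away is the contradiction. Repairing the syntax would not by itself change the outcome or remove the Week 2-12 terms. Two passages send the reader to this appendix, and no block in it carries the stated primary analysis from imputation to pooled result.

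**Conclusion.** The contradiction is established from the documents alone and needs no assumption: the pooling code has the wrong outcome, post-randomisation covariates, and no means of producing the LS mean differences that the text pools. It is a drafting error worth correcting, not evidence that the final analysis would be wrong.

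The consequence is conditional. If the listed terms survived a repair, the coefficient would answer a different question from the Section II.A estimand, usually with lower power, though a late-emerging effect can leave power unchanged or raise it. False positives are not the issue when there is no effect at any visit. The size cannot be determined, because the planning values are redacted and neither visit correlations nor the time course of effect is given; the figures above are illustrations only.

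**What to change.** Replace the pooling block in SAP Appendix II:

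- In each imputed dataset derive percent change = 100 x (`week16` - `base_EASI`)/`base_EASI`.
- By `_imputation_`, fit it on `trt01p` (CLASS, reference placebo), `base_VIGA` and `prioruse` as factors, and `base_EASI` as covariate.
- Output LS means and LS mean differences with standard errors, and pool those in PROC MIANALYZE.
- Keep Weeks 2-12 in the imputation step only.

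In the separate ANCOVA example, change `chg` to percent change and the reference level from vehicle to placebo. Add one sentence saying that the Section VI text governs if code and text differ.

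The cost is appendix wording; no data, visits or patients are affected. SAP Section I.B allows changes until treatment unblinding, so this should be done before the unblinded Week 16 analysis described in Section IV.F.
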